- 11. Have alanine aminotransferase (ALT) or aspartate aminotransferase (AST) levels ≥2 x upper limit of normal (ULN) or a bilirubin level 1.5 x ULN unless due to a documented history of Gilbert's syndrome
- 12. Estimated glomerular filtration rate (eGFR) ≤60 mL/min/1.73m² as calculated by the Chronic Kidney Disease Epidemiology Collaboration [CKD-EPI] 2009 creatinine equation at Visit 1 (Screening)
- Positive hepatitis C virus (HCV) antibody (Ab), hepatitis B surface antigen (HBs Ag), hepatitis A virus (HAV) IgM antibody (HAV-Ab [IgM]) or human immunodeficiency virus (HIV) test at Visit 1 (Screening)

BTRX-335140	
Clinical Study Protocol Amendment 7	

- 14. Have a thyroid-stimulating hormone (TSH) level of <0.9 x lower limit of normal (LLN) or >1.2 x ULN on or off stable treatment for hyperthyroidism or hypothyroidism; if TSH is abnormal, evaluate reflex Free T3 and Free T4. If reflex testing is normal, the assessment of normal thyroid function will be determined based on the judgement of the investigator, following discussion with the medical monitor.
- 15. Have any other clinically significant abnormalities (significant would include laboratory deviations requiring acute medical intervention or further medical evaluation) in laboratory results at screening, including clinical chemistries, hematology, and urinalysis, and any clinical information that, in the judgment of the investigator or Sponsor, should preclude a subject's participation at study entry
- 16. Exclusionary ECG abnormalities obtained at Visit 1 (Screening) or Visit 2 (Baseline) are QT interval corrected using Fridericia's formula (QTcF) >450 msec in males or >470 msec in females, complete bundle branch block, evidence of myocardial infarction or ischemia, and predominantly nonsinus conducted rhythms. Other abnormalities can be exclusionary at the discretion of the principal investigator or medical monitor. See Section 6.3.5 of protocol for guidance on ECG interpretations.
- 17. Have a positive urine drug screen for amphetamines, barbiturates, cocaine, methadone, opioids, propoxyphene, tetrahydrocannabinol (THC), phencyclidine, or a positive blood alcohol level assessed by breathalyzer at Visit 1 (Screening) and Visit 2 (Baseline). For occasional (1 to 2 times per month maximum) cannabis users only, 1 retest is allowed and subject must agree to abstain from use for the duration of the study; a positive second test is exclusionary.
- 18. Have any use, by history, of Salvinorin A

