Barbiturates	Hepatitis B Core Antibody (HBc Ab)
Benzodiazepines	Hepatitis C Antibody (HC Ab)
Delta-9-tetrahydrocannabinol (THC)	Hepatitis A Antibody (HAV-Ab [IgM])
Cocaine	Human immunodeficiency virus (HIV)
Ethyl alcohol (via breathalyzer)	
Opioids	
Phencyclidine	
Propoxyphene	
Methadone	
Thyroid function ^d :	
Thyroid-stimulating hormone (TSH); if abnormal perform	
Free T3 and Free T4 reflex testing	

BTRX-335140
Clinical Study Protocol Amendment

Pregnancy Test (females of child bearing potential only) ^e	
^a Performed at each visit.	

- To be conducted at baseline only, unless indicated for hepatic monitoring testing (see Table 3)
- ^c Creatine kinase is to be fractionated if CK results >1000 IU/L.
- ^d Screening only.

^e Serum pregnancy test at Visit 1 (Screening) is to be performed by a Sponsor-designated laboratory; urine pregnancy tests will be performed at all subsequent visits by the site.

^f Baseline only; optional collection.

Note: All safety laboratory tests will be analyzed by a Sponsor-designated laboratory, unless otherwise specified.

6.3.2.2 Hepatic Safety and Enhanced Hepatic Testing

7

Bilirubin, ALT, and AST will be measured at each scheduled visit (as part of the scheduled clinical laboratory tests). If a subject has elevated ALT or AST (>3 x ULN) or elevated total bilirubin (>2 x ULN), the following procedures must be performed:

- 1. Contact the medical monitor/Sponsor to assess whether the subject should be discontinued from study drug (see Section 4.4).
- 2. Perform clinical laboratory testing according to the list of hepatic monitoring tests in Table 3 within 48 to 72 hours. The frequency of repeat testing to be performed will be determined in consultation with the medical monitor/Sponsor. In general, repeat laboratory testing should be performed 2 to 3 times per week; frequency of retesting can decrease to once a week or less if, the laboratory abnormality(ies) stabilizes and/or subject is asymptomatic.
- 3. Provide additional history from the subject including:
 - history of concomitant medication (prescription, nonprescription, over-the-counter, herbal supplements, dietary supplements)
 - alcohol use, recreational drug use, and special diets
 - recent illnesses, exposures, and exposures to environmental chemical agents

These results will be reviewed in a timely fashion by the Sponsor-designated medical monitor, along with the subject's clinical case, to determine possible cause.

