7.5.4 Clinical Laboratory Evaluation

All descriptive summaries of laboratory results will be based on data analyzed by the central laboratory and presented in Système International (SI) units, as suggested by the Center for Biologics Evaluation and Research and the Center for Drug Evaluation and Research *Position on Use of SI Units for Lab Tests* (Oct 2013). All data will be included in by-subject data listings. Laboratory measurements identified as abnormal (ie, outside the normal range) will also be listed separately.

BlackThorn Therapeutics, Inc.	Statistical Analysis Plan
K2-MDD-201	Version 2.0; 03 June 2022

Clinical laboratory measurements, including serum chemistry and hematology, will be summarized by treatment group. Descriptive statistics will be presented for observed values and changes from baseline at each visit where parameters were scheduled to be collected per the clinical study protocol.

Where applicable, laboratory results will be classified as "low," "normal," or "high" with respect to the parameter-specific reference ranges (ie, below the lower limit of the normal range, within the normal range, or above the upper limit of the normal range). Three-by-three contingency tables will be presented for each laboratory parameter to summarize the shift from the baseline category to the worst post-baseline measurement, defined as the value numerically farthest outside of the normal range across all post-baseline visits through the end of the study. Summary results will include the count and percentage of subjects within each shift category and treatment group.

The number and percentage of subjects with a PCS (potentially clinically significant) laboratory result for the select analytes listed below in

will be presented by treatment group and study visit. PCS laboratory results will also be listed.

Analyte	PCS Cutoffs
Hemoglobin	Low:< 10.0 g/dL; < 6.2 mmol/L; <100 g/L
	High: > 2 g/dL (20 g/L) above ULN or above baseline if
	baseline is above ULN
Platelets count	<75,000/mm3; <75.0 x 10e9 /L
WBC count	<3000/mm3; <3.0 x 10e9 /L
Neutrophils	<1500/mm3; <1.5 x 10e9 /L
Lymphocytes	Low: < 800/mm3; < 0.8 x 10e9 /L
	High: >4000/mm3 - 20,000/mm3; > 4 x 10e9 /L - 20 x 10e9 /L
Total bilirubin	> 1.5 x ULN
AST	> 3.0 x ULN
ALT	> 3.0 x ULN
Alkaline phosphatase	> 3.0 x ULN
Creatinine	> 1.5 x above baseline; > 1.5 x ULN
Sodium	Low: < 130 mmol/L
	High: > 150 mmol/L
Potassium	Low: < 3.0 mmol/L
	High: > 5.5 mmol/L
СК	> 5 x ULN
GGT	>2.5 x ULN

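### SAP Table 5 counts total bilirubin above 1.5 x ULN without reference to baseline, so elevations admitted under the Gilbert's exception count as PCS at on-treatment visits

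*Protocol*

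**What the plan says.** - **Entry rule.** Exclusion 11, in the Protocol Synopsis and again in Section 4.1.2, reads "a bilirubin level 1.5 x ULN unless due to a documented history of" Gilbert's syndrome. Neither place prints a comparator before 1.5 x ULN, and the exception has no upper limit.
- **PCS rule.** SAP 7.5.4 states: "The number and percentage of subjects with a PCS (potentially clinically significant) laboratory result for the select analytes listed below in" Table 5 "will be presented by treatment group and study visit. PCS laboratory results will also be listed". The bilirubin row is "Total bilirubin > 1.5 x ULN", with no baseline term and no mention of Gilbert's syndrome.
- **Other Table 5 rows.** High hemoglobin does look back: "High: > 2 g/dL (20 g/L) above ULN or above baseline if" the baseline value is above ULN. Creatinine is "> 1.5 x above baseline; > 1.5 x ULN", a baseline-relative term beside an absolute one. Most other rows, including AST, ALT, alkaline phosphatase, GGT and CK, are purely absolute.
- **Other laboratory output in SAP 7.5.4.** Change from baseline at each visit, a low/normal/high shift table from baseline to worst post-baseline value, and listings of all data.
- **Time window.** SAP 7.5 defines the treatment-emergent period by time alone, from first dose to 30 days after last dose. SAP 7.1.5 takes baseline as the last value before dosing.
- **Hepatic work-up.** Protocol 6.3.2.2, for "elevated total bilirubin (>2 x ULN), the following procedures must be performed", also has no Gilbert's exception.

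**The concern.** The entry exception and the safety flag meet at the same figure. Subjects with documented Gilbert's syndrome may enter above 1.5 x ULN, and the same level makes them PCS at each later visit where the value stays above it, whether bilirubin has risen, stayed level or fallen. The by-visit count therefore mixes two things: who was admitted under the exception, and what happened after dosing.

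Small-count safety tables are read for imbalance between arms. A difference of two or three subjects in this row could reflect only how the pre-existing elevations fell at randomization, and a background count in both arms makes a genuine new elevation harder to see.

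The SAP already handles this kind of problem elsewhere. High hemoglobin resets to baseline, and SAP 7.5.5.3 repeats the corneal summaries without subjects who had endothelial dystrophy before treatment.

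**Working it through.** The documents give no figure on this point, so there is none to reproduce. The check has two parts.

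**1. Apply the rules to example values** (multiples of ULN; the values are illustrations).

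| Baseline | On treatment | PCS as written (>1.5) | PCS if baseline must be not >1.5 | Shift table |
|---|---|---|---|---|
| 1.5 | 1.5 | no | no | high to high |
| 1.6 | 1.6 | yes | no | high to high |
| 2.0 | 2.0 | yes | no | high to high |
| 2.0 | 1.6 | yes | no | high to high |
| 1.0 | 1.6 | yes | yes | normal to high |

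A stable or falling elevation counts in the same way as a new one. The shift table shows that the value was high at entry, but it puts stable, falling and rising values in one cell.

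**2. Size of the noise.** Inputs: about 180 subjects randomized 1:1 (Protocol 3.1), so n = 90 per arm. The share q of subjects who enter above 1.5 x ULN under the exception and stay there is an **assumption**, because the documents give no number. There is no drug effect. With A and B the counts in the two arms, each Binomial(90, q):

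- expected count per arm = 90q
- P(|A − B| ≥ 3) = Σ P(A = a) × P(B = b), summed over all pairs with |a − b| ≥ 3

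| Assumed q | 90q | P(difference of 3 or more) |
|---|---|---|
| 0.5% | 0.45 | 0.014 |
| 1% | 0.9 | 0.060 |
| 2% | 1.8 | 0.173 |
| 4% | 3.6 | 0.334 |
| 8% | 7.2 | 0.489 |

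At 0.5% the effect is negligible. It becomes appreciable from about 2% upward.

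**3. Check on a possible repair.** One option is to replace the flag, for subjects already above the cut-off, with a rise to more than 1.5 x their own baseline. A subject at 1.6 x ULN would then need more than 1.5 × 1.6 = 2.4 x ULN. A rise to 2.3 x ULN would not be flagged, although it crosses the >2 x ULN trigger in Protocol 6.3.2.2. Replacing the absolute flag would hide such a rise, so the repair should add to the existing count.

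**The case against.** The strongest reply is that Table 5 is a plain absolute screen, as most of its rows are, and that SAP 7.5.4 already compares with baseline in other ways. A subject stable at 2.0 x ULN shows zero change and high-to-high, and every value is listed. The laboratory PCS rule, unlike the ECG rule in SAP 7.5.5.2, is not limited to post-baseline visits, so a baseline column is possible. Creatinine is only a partial precedent, because its second term is absolute.

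Much of this stands, and it makes the point a small one. It does not correct the count. Group mean change dilutes a few subjects, the shift cell does not separate stable from rising values, and a baseline column does not link each later flag to the same subject's baseline.

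Stronger readings are tempting, but the documents do not support them:

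- *A reader might infer that pre-existing values are reported as on-treatment liver findings.* The SAP calls them PCS laboratory results. Laboratory adverse events depend on the investigator's judgement of clinical significance (SAP 6.4.2.4), and the events of special interest cover only skin and eye disorders (SAP 6.4.2.3).
- *A reader might infer bias against the drug.* The exception applies to both arms under 1:1 randomization, so it adds noise.
- *A reader might infer loss of power.* No test is planned on PCS counts.
- *A reader might take the entry limit as at or above 1.5 x ULN.* No comparator is printed, and exactly 1.5 x ULN is not PCS.

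**Conclusion.** The point holds as a minor reporting gap. Exclusion 11 can admit bilirubin above 1.5 x ULN in documented Gilbert's syndrome, and Table 5 then counts that value as PCS at on-treatment visits even if it is stable or falling. The effect is noise in one descriptive safety row. The primary analysis, sample size and alpha are not affected.

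The size rests entirely on the assumed share of such subjects. The probability of a chance difference of 3 or more runs from about 0.01 at 0.5% to 0.49 at 8%, and the documents do not say where in that range, or outside it, the trial falls. The calculation also assumes 90 per arm, values that stay above the cut-off, and no drug effect.

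Protocol 6.3.2.2 raises a separate consistency question. A subject admitted under the exception above 2 x ULN meets its mandatory trigger without any change from entry.

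**What to change.** In SAP 7.5.4 and Table 5:

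1. Keep the absolute total bilirubin count and the PCS listing as they are.
2. Add a treatment-emergent row: post-baseline total bilirubin >1.5 x ULN in subjects whose baseline was not >1.5 x ULN.
3. Show by arm the number already >1.5 x ULN at baseline, and give those subjects' change from baseline separately so that further rises stay visible.

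Define the new row on the baseline value, not on the diagnosis. It then needs no new data, since total bilirubin is already collected at screening and baseline. The cost is a few lines of SAP text and programming and one or two extra table rows.

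In the Protocol, the sponsor should print the comparator intended in exclusion 11, and should reconcile the Gilbert's exception with the >2 x ULN trigger in Section 6.3.2.2. No clinical rule is proposed here.

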BTRX-335140	BlackThorn Therapeutics, Inc.
Clinical Study Protocol Amendment 7	Date: 24Jan2022
LIST OF TABLES	

Table 1:	Summary of Changes
Table 2:	Clinical Laboratory Tests
Table 3:	Hepatic Monitoring Tests

LIST OF FIGURES

Figure 1:	Study Design	29
-		

LIST OF APPENDICES

Appendix 1:	Guidance for Virtual Visits	(Via Telephone)
Appendix 2:			87

BTRX-335140	
Clinical Study Protocol Amendment 7	

LIST OF ABBREVIATIONS

Abbreviation	
or Term	Definition
Ab	antibody
ADD	attention deficit disorder
ADHD	attention deficit hyperactivity disorder
AE	adverse event
ALT	alanine aminotransferase
APA	American Psychiatric Association
AESI(s)	adverse event(s) of special interest
AST	aspartate aminotransferase
ANCOVA	analysis of the covariance
AUC	area under the curve
AUD	alcohol use disorder
BMI	body mass index
BP	blood pressure
CAT	Clinical Assessment Technology
CFR	Code of Federal Regulations
cGCP	current Good Clinical Practice
CGI-I	Clinical Global Impression of Improvement
CGI-S	Clinical Global Impression of Severity
CI	confidence interval
CIOMS	Council for International Organizations of Medical Sciences
CKD-EPI	Chronic Kidney Disease Epidemiology Collaboration
C _{max}	maximum plasma drug concentration
CNS	central nervous system
COVID-19	coronavirus disease 2019
COWS	Clinical Opiate Withdrawal Scale
CREB	cAMP response binding protein
CRF	case report form
CRO	Contract Research Organization
C-SSRS	Columbia Suicide Severity Rating Scale
DSM-5	Diagnostic and Statistical Manual of Mental Disorders Fifth Edition
DSM-IV-TR	Diagnostic and Statistical Manual of Mental Disorders, Fourth Edition, Text Revision
EC	Ethics Committee
ECG	electrocardiogram, electrocardiographic
eCRF	electronic case report form
EDC	electronic data capture
eGFR	estimated glomerular filtration rate

BTRX-335140 Clinical Study Protocol Amendment 7

Abbreviation	Definition
FDA	Definition Ecod and Drug Administration
GAD	rood and Diug Administration
GAD	generalized anxiety disorder
	generalized estimating equations
HADS	Hospital Anxiety and Depression Scale
HADS-A	Hospital Anxiety and Depression Scale – Anxiety Subscale
HADS-D	Hospital Anxiety and Depression Scale – Depression Subscale
HAM-A	Hamilton Anxiety Rating Scale
HAMD-1/	Hamilton Depression Rating Scale – 1/-item Version
HAV	hepatitis A virus
HAV-Ab (lgM)	hepatitis A virus antibody
HBs Ag	hepatitis B surface antigen
HCV	hepatitis C virus
HIPAA	Health Insurance Portability and Accountability Act
HIV	human immunodeficiency virus
HPMC	hydroxypropyl methylcellulose
IB	investigator's brochure
IC ₅₀	half-maximal inhibitory concentration
ICC	intraclass correlation coefficient
ICF	informed consent form
ICH	International Council for Harmonisation of Technical Requirements for Pharmaceuticals for Human Use
IEC	Independent Ethics Committee
IgM	immunoglobulin M
IND	US Investigational New Drug Application
IRB	Institutional Review Board
IWRS	interactive web-response system
KOR	kappa opioid receptor
KORA	kappa opioid receptor antagonist
LC-MS/MS	liquid chromatography-tandem mass spectrometry
LLN	lower limit of normal
LS Means	least-square means
MedDRA	Medical Dictionary for Regulatory Activities
MDD	major depressive disorder
MMRM	mixed-models repeated measures
NOAEL	no-observed-adverse-effect-level
PDF	portable document format
PET	positron emission tomography

BTRX-335140	BlackThorn Therapeutics, Inc.
Clinical Study Protocol Amendment 7	Date: 24Jan2022

Abbreviation	Definition
or Term	
POC	proof of concept
pp	proof of concept
PTSD	nost_traumatic stress disorder
OD	once daily
OTcF	Fridericia's correction method for OT Interval
REB	Research Ethics Board
RO	
KO	
SAE	serious adverse event
SAP	statistical analysis plan
SCID-5-CT	Structured Clinical Interview for DSM-5 Disorders Clinical Trials Version
SD	standard deviation
SDS	Sheehan Disability Scale
SHAPS	Sneth-Hamilton Pleasure Scale
SIGH-A	Structured Interview Guide for the Hamilton Anyiety Rating Scale
SIGH-D	Structured Interview Guide for the Hamilton Depression Rating Scale
SNRI	serotonin noreninenbrine reuntake inhibitor
SOP	Standard Operating Procedure
SSRI	selective serotonin reuntake inhibitor
SUSAR	serious unexpected suspected adverse reaction
ТС	telephone call
TEAE	treatment-emergent adverse event
ТНС	tetrahydrocannabinol
ТРО	third-party organization
TSH	thyroid-stimulating hormone
UDS	urine drug screen
ULN	upper limit of normal
US	United States
WHO	World Health Organization
WHODrug	World Health Organization Drug classification

BTRX-335140	
Clinical Study Protocol Amendment 7	

1 INTRODUCTION

1.1 Background Information

1.1.1 Major Depressive Disorder

Major depressive disorder (MDD) is the most common mood disorder and imposes considerable economic and humanitarian suffering, such as decreased quality of life, functional impairment, and increased mortality rate. Currently, MDD is the leading cause of disability and afflicts approximately 322 million people worldwide (4.4% of the global population), with prevalence increasing 18% between 2005 and 2015 (World Health Organization [WHO] 2017). By 2020, depressive disorders are expected to be the second highest cause of morbidity in the world (Murray and Lopez 2006) and have been predicted to become the leading cause of disease burden by the year 2030 (WHO 2004). The lifetime prevalence of MDD is approximately 16.6% in the United States (US) (Kessler et al 2003). Episodes of MDD are often chronic and recurrent, with a relapse chance rate of 55% to 90% for individuals who experienced one or two prior depressions. More than 80% of the individuals who experience a second episode and who are not treated will experience a third episode within 3 years (Thase and Sullivan 1995).

A clinical diagnosis of MDD is made based on the continuous presence of at least 5 of 9 symptoms over at least 2 weeks. One of these symptoms, as defined in the Diagnostic and Statistical Manual of Mental Disorders, 5th Edition (DSM-5), must be either depressed mood or anhedonia, which is defined as diminished interest or pleasure in response to rewarding stimuli (APA 2013). This diagnostic classification assigns equal importance to depressed mood and anhedonia thus highlighting anhedonia as a core feature of the disorder. The classification system also acknowledges that anhedonia may be present in a subset of individuals with MDD. Estimates of significant anhedonia among patients with MDD are rare; 1 report describes an anhedonia rate of approximately 37% among a sample of 65 individuals diagnosed with MDD (Pelizza and Ferrari 2009). Moreover, published data indicate that the presence of anhedonia may represent a distinct physiologically based subset of patients with MDD, as evidence from functional neuroimaging assessments indicates that anhedonia is linked to disruptions in central reward system functioning and is an important aspect of depression pathophysiology (Keedwell et al 2005). This is an important finding from the standpoint of therapeutic interventions because the presence of anhedonic symptoms has been found to be associated with poorer longitudinal symptom progression among patients with depression (Morris et al 2009) and is a major predictor of suicide (Fawcett et al 1990; Winer et al 2014).

1.1.2 Treatments

The current mainstays of pharmacological treatments for depression include the use of selective serotonin reuptake inhibitors (SSRIs) (Fava et al 2007; Zupancic and Guilleminault 2006) and serotonin-norepinephrine reuptake inhibitors (SNRIs) (Stahl et al 2005), which provide reasonable treatment options; however, these therapies are not effective in all patients, and are often associated with undesirable side effects, such as weight gain and sexual dysfunction. The lack of efficacy and the adverse events (AEs) associated with the use

BTRX-335140	BlackThorn Therapeutics, Inc.
Clinical Study Protocol Amendment 7	Date: 24Jan2022

of these antidepressants lead to high levels of treatment discontinuation (Zajecka 2000). Even with multiple consecutive treatments, only a small proportion of patients remain asymptomatic (Rush 2007). Thus, there continues to be a substantial unmet medical need for new antidepressants with greater response rates and improved tolerability.

The presence of anhedonia is associated with difficulty in treating MDD. Research findings indicate that available therapies such as SSRIs do not target depression-related motivational and reward-processing deficits sufficiently (APA 2000; Dunlop and Nemeroff 2007; McCabe et al 2010; Nutt et al 2007; Price et al 2009; Shelton and Tomarken 2001) and that anhedonic symptoms predict inadequate treatment response (Spijker et al 2001).

The presence of anhedonia is associated with inadequate treatment response to antidepressant drugs (McMakin et al 2012; Uher et al 2012) and potentially also to psychological treatments (Craske et al 2016). Unfortunately, research findings indicate that available therapies such as SSRIs do not target depression-related motivational and reward-processing deficits sufficiently (APA 2000; Dunlop and Nemeroff 2007; McCabe et al 2010; Nutt et al 2007; Price et al 2009; Shelton and Tomarken 2001). For these reasons, recent efforts have been directed towards developing therapies that effectively target anhedonia, such as ketamine and Positive Affect Treatment (Craske et al 2016; Lally et al 2014).

